2.4.3.2 Compliance

A given administration will be considered noncompliant if the patient did not take the planned dose of treatment as required by the protocol. No imputation will be made for patients with missing or incomplete data.

Percentage of compliance for a patient will be defined as the number of administrations that the patient was compliant divided by the total number of administrations that the patient was planned to take during the treatment epoch defined in [Section 2.1.3.2.2.1](#).

Treatment compliance percentages will be summarized descriptively as quantitative variables (number, mean, SD, median, minimum, and maximum). The percentage of patients whose compliance is <80% will be summarized in [Section 2.4.4.5](#).

Cases of overdose (defined as at least twice the intended dose during an interval of less than 11 days) will constitute serious adverse events and will be listed as such.

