#### **8.3.1 Adverse event of special interest**

An adverse event of special interest (AESI) is an AE (serious or nonserious) of scientific and medical concern specific to the Sponsor's product or program, for which ongoing monitoring and immediate notification by the Investigator to the Sponsor is required. Such events may require further investigation in order to characterize and understand them. Adverse events of special interest may be added, modified or removed during a study by protocol amendment.

For these AESIs, the Sponsor will be informed immediately (ie, within 24 hours), per SAE notification described in [Section 8.3.2](#), even if not fulfilling a seriousness criterion, using the corresponding pages in the CRF (to be sent) or screens in the e-CRF. If an SAE or any AESI of anaphylactic reactions or systemic allergic reactions that are related to IMP and require treatment, or severe injection site reactions lasting longer than 24 hours, occurs in a patient, blood samples should be collected for determination of functional dupilumab concentration, and ADA assessment at or near the onset and completion of the occurrence of the event, if possible (see [Section 8.5.1.3](#) for details).

- Clinically symptomatic eosinophilia (or eosinophilia associated with clinical symptoms)
- Anaphylactic reactions or systemic allergic reactions that are related to IMP and require treatment (see Appendix 15, [Section 10.15](#))
- Severe injection site reactions that last longer than 24 hours
- Any infection meeting at least one of the following criteria:
  - Any serious infection (SAE)
  - Requires parenteral (intravenous, intramuscular, subcutaneous) antimicrobial therapy

- Requires oral antimicrobial therapy for longer than 2 weeks
- Is a parasitic infection
- Is an opportunistic infection (see Appendix 16, [Section 10.16](#))

Note: antimicrobial therapy refers to antibiotic, antiviral, and antifungal agents

- Significant ALT elevation
  - ALT >5 x the upper limit of normal (ULN) in patients with baseline ALT  $\leq$  2 x ULN; or
  - ALT >8 x ULN if baseline ALT >2 x ULN
- Pregnancy of a female subject entered in a study as well as pregnancy occurring in a female partner of a male subject entered in a study with IMP/NIMP;

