  - Pregnancy occurring in a female patient entered in the clinical trial or in a female partner of a male patient entered in the clinical trial. It will be qualified as an SAE only if it fulfills one of the seriousness criteria (see Appendix 3 [[Section 10.3](#)]).
  - In the event of pregnancy in a female participant, IMP should be discontinued.
  - Follow-up of the pregnancy in a female participant or in a female partner of a male participant is mandatory until the outcome has been determined (see Appendix 4 [[Section 10.4](#)])
  - Abnormal pregnancy outcomes (eg, spontaneous abortion, fetal death, stillbirth, congenital anomalies, ectopic pregnancy) are considered SAEs
- Symptomatic overdose (serious or nonserious) with IMP/NIMP
- An overdose (accidental or intentional) with the IMP is an event suspected by the Investigator or spontaneously notified by the patient and defined as at least twice the intended dose during an interval of less than 8 days. The circumstances (ie, accidental or intentional) should be clearly specified in the verbatim and symptoms, if any, entered on separate adverse event forms.
- An overdose (accidental or intentional) with any NIMP is an event suspected by the Investigator or spontaneously notified by the patient and defined as at least twice the maximum daily dose as specified in a drug label, within the intended therapeutic interval. "The circumstances (ie, accidental or intentional) should be clearly specified in the overdose form".

The definitions of an AE or SAE can be found in Appendix 3 ([Section 10.3](#)).

Adverse event will be reported by the participant (or, when appropriate, by a caregiver, surrogate, or the participant's legally authorized representative).

The Investigator and any qualified designees are responsible for detecting, documenting, and recording events that meet the definition of an AE or SAE and remain responsible for following up AEs that are serious, considered related to the study intervention or study procedures, or that caused the participant to discontinue the study ([Section 7](#)).

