## **8.4 TREATMENT OF OVERDOSE**

Overdose is an AESI (defined in [Section 8.3.1](#)). No antidote is available for dupilumab.

In the event of an overdose, the Investigator/treating physician should:

1. Contact the Medical Monitor immediately.
2. Closely monitor the participant for any AE/SAE and laboratory abnormalities until study intervention can no longer be detected systemically.
3. Obtain a serum sample for PK analysis as soon as possible from the date of the last dose of study intervention if requested by the Medical Monitor (determined on a case-by-case basis).
4. Document the quantity of the excess dose as well as the duration of the overdose in the CRF.

Decisions regarding dose interruptions or modifications will be made by the Investigator in consultation with the Medical Monitor based on the clinical evaluation of the participant.

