**A SAE is defined as any untoward medical occurrence that, at any dose:**

**a) Results in death**

**b) Is life-threatening**

The term 'life-threatening' in the definition of 'serious' refers to an event in which the participant was at risk of death at the time of the event. It does not refer to an event, which hypothetically might have caused death, if it were more severe.

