### **Assessment of intensity**

The Investigator will make an assessment of intensity for each AE and SAE reported during the study and assign it to 1 of the following categories:

- **Mild:** An event that is easily tolerated by the participant, causing minimal discomfort and not interfering with everyday activities.
- **Moderate:** An event that causes sufficient discomfort and interferes with normal everyday activities.

- Severe: An event that prevents normal everyday activities. An AE that is assessed as severe should not be confused with a SAE. Severe is a category utilized for rating the intensity of an event; and both AEs and SAEs can be assessed as severe.

An event is defined as 'serious' when it meets at least 1 of the predefined outcomes as described in the definition of an SAE, NOT when it is rated as severe.

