Anaphylactic reaction	Anaphylactic reaction algorithmic approach (Introductory Guide for Standardised MedDRA Queries (SMQs) Version 18.1): includes anaphylactic reaction narrow SMQ (20000021) terms and programmatic identification of cases based on occurrence of at least two preferred terms meeting the algorithm criteria occurring within 24 hours of each other. The latter cases identified using the algorithm will undergo blinded medical review taking into account the timing of events relative to each other and to IMP administration for final determination of an anaphylactic reaction or not.
Hypersensitivity (medically reviewed)	SMQ hypersensitivity (20000214) narrow search or PT in (Pruritus, Pruritus generalized) and [AE corrective treatment/therapy='Y' or Action taken with IMP='Drug withdrawn' or Action taken with IMP='Drug interrupted'] followed by blinded medical review (documented process) for selection of relevant systemic hypersensitivity events
Serious injection site reactions or severe injection site reactions that last longer than 24 hours	HLT = 'Injection site reaction' and either with serious status, or with severe status and (AE end date/time - AE start date/time) ≥ 24 hours or ongoing
Severe or serious infection	Primary SOC = 'Infections and infestations' and with severe or serious status
Parasitic infection	The Infection Type 'Parasitic' was checked on eCRF page "Infection Defined as AESI Complementary Form"
Opportunistic infection	The Infection Type 'Opportunistic' was checked on eCRF page "Infection Defined as AESI Complementary Form"
Drug-related hepatic disorder	Drug-related hepatic disorders-Comprehensive search narrow SMQ (20000006)
Pregnancy	Primary SOC = 'Pregnancy, puerperium and perinatal conditions' or PT in (Aborted pregnancy, False negative pregnancy test, Pregnancy test positive, Pregnancy test urine positive, Ectopic pregnancy termination)
Symptomatic overdose with IMP	Symptomatic Overdose is answered Yes, with Overdose of IMP answered Yes on AE eCRF.
Symptomatic overdose with NIMP	Symptomatic Overdose is answered Yes, with Overdose of NIMP answered Yes on AE eCRF.
Eosinophilia	HLT = 'Eosinophilic disorders' or PT = 'Eosinophil count increased'
Other selected AE grouping	
Injection site reaction	HLT = 'Injection site reaction'
Malignancy	Sub-SMQ (20000091)– Malignant or unspecified tumors
Suicidal behavior	PT in (Completed suicide, Suicidal ideation, Depression suicidal, Suicidal behavior, Suicide attempt)

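### In the documents as supplied, the SAP and protocol disagree on what counts as an IMP overdose and whether it is automatically an SAE, and protocol Appendix 3 gives opposite rules on lack of efficacy.

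*SAP*

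**What the plan says.** **Version.** SAP Section 1.5 refers to protocol amendment 7. The supplied protocol appears to be another version. Its Section 6.3.1 stratifies by asthma history where SAP Section 1.1 stratifies by ICS dose, and its Table 1 has two primary endpoints where SAP Section 2.1.3.1 has one.

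**IMP overdose.**
- SAP 2.4.3.2 (Compliance): "Cases of overdose (defined as at least twice the intended dose during an interval of less than 11 days) will constitute serious adverse events". It adds that they are listed on that basis.
- Protocol 8.3.1: IMP overdose is "defined as at least twice the intended dose during an interval of less than 8 days". The AESI entry reads "Symptomatic overdose (serious or nonserious) with IMP/NIMP".
- Protocol 8.4: "Overdose is an AESI", here without the restriction to symptomatic cases.
- Protocol 8.3.1 on the category as a whole: "An adverse event of special interest (AESI) is an AE (serious or nonserious) of scientific and medical concern".
- Protocol Appendix 3: an event is serious "when it meets at least 1 of the predefined outcomes as described in the definition of an SAE". The named outcomes do not include overdose.
- SAP Table 2 identifies the IMP overdose AESI when "Symptomatic Overdose is answered Yes, with Overdose of IMP answered Yes on AE eCRF". It sets no interval and no seriousness condition.

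**Lack of efficacy.** Both statements are in protocol Appendix 3, under the events that meet the AE definition. One bullet says that lack of efficacy in itself is not reported as an AE or SAE and is captured by the efficacy assessments. The next bullet says that it does count as an AE or SAE.

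**The concern.** A safety programmer working from SAP 2.4.3.2 and a site working from protocol 8.3.1 would not identify the same overdoses and would not give them the same seriousness. Followed literally, the SAP sentence puts overdoses that meet no seriousness criterion into an SAE listing, for example an accidental early injection without symptoms. The programmer is not told whether to use the seriousness recorded on the AE form or to override it.

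The lack-of-efficacy bullets give sites two opposite instructions in the same list, and neither is marked as prevailing. At stake are a consistent SAE listing and a single reporting instruction. No efficacy result is involved.

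**Working it through.** The plan gives no figure to reproduce. The check sets the texts side by side and does day arithmetic on the two intervals. I count the interval as the number of days from one injection to the next.

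**1. Which gaps count as an overdose (two full doses)?**

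| Gap in days | Protocol 8.3.1 (under 8) | SAP 2.4.3.2 (under 11) |
|---|---|---|
| up to 7 | overdose | overdose and SAE |
| 8, 9, 10 | not an overdose | overdose and SAE |
| 11 or more | not an overdose | not an overdose |

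The thresholds differ by 11 − 8 = 3 days. The disagreement runs one way: no gap is an overdose under the protocol only.

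**2. Can dosing within the permitted window fall in the disputed range?** Protocol Table 2 and Section 6.1.1 give a dose every 14 ± 3 days. Note a to the schedule in Section 1.3.1 applies ± 3 days to the visit schedule in the treatment period. These allow two readings:
- Measured dose to dose, the gap runs from 14 − 3 = 11 to 14 + 3 = 17 days. Neither rule flags in-window dosing.
- Measured around fixed scheduled days, one dose 3 days late followed by one 3 days early gives 14 − 6 = 8 days. The longest gap is 14 + 6 = 20 days. In-window doses 8, 9 or 10 days apart would be SAEs under the SAP and not overdoses under the protocol.

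Each threshold equals the shortest permitted gap under one of these readings. The documents do not say which reading applies.

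**3. Seriousness.** This conflict does not depend on the interval. For gaps up to 7 days both documents see an overdose. The SAP makes each one an SAE; the protocol leaves seriousness to the outcome test in Appendix 3 and expressly allows nonserious symptomatic overdose. Within the SAP, Table 2 sets no seriousness condition, and Section 2.4.5.1 counts patients with serious treatment-emergent events separately from all treatment-emergent events for each AESI. If the 2.4.3.2 rule were carried into those rows, they would hold the same patients for any symptomatic overdose within its definition.

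**4. Lack of efficacy.** Both bullets agree that the signs, symptoms and consequences are reported if they meet the AE or SAE definition. They differ on lack of efficacy itself: one excludes it and the other includes it. For COPD worsening, protocol Sections 8.1.1.1 and 8.3.8 and the first item in Appendix 3 under events not meeting the AE definition already give a rule: an exacerbation is not an AE unless it is serious. The unresolved part is therefore lack of efficacy as such.

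**The case against.** **Version.** The strongest objection is that amendment 7 may carry the same overdose wording as the SAP. That stands: the SAP-to-protocol comparison holds only for the documents supplied. The SAP's own table of modifications does not settle it, because it covers the statistical section. The poor fit inside the SAP and the clash inside Appendix 3 do not depend on this comparison.

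**Reach.** The SAP sentence sits in the compliance section and says only that cases are listed. The protocol has the investigator record AEs and SAEs, and nothing in SAP 2.4.5.1 brings the overdose rule into the SAE tables or recodes seriousness. This also stands. The AESI rows are generic, and overlap between them is not in itself a contradiction.

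**Open-ended SAE definition.** Appendix 3 lets medical judgment make other events serious, so the absence of overdose from the list proves little. That is fair, but case-by-case judgment is not an automatic rule. The protocol's wording on nonserious overdose is the better evidence.

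**Stronger readings.** A reader might infer that expedited reporting is affected. It is not, because protocol Sections 8.3.1 and 8.3.2 require AESIs to be notified within 24 hours whether or not they are serious. A reader might also infer that hospitalised COPD events could drop out of SAE reporting, from the example given at the start of the SAE definition in Appendix 3. The documents do not support that. The sentence covers only events that are not AEs, and the COPD provisions cited above make a serious exacerbation reportable.

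**Conclusion.** Two safety-reporting rules conflict in the supplied text, and both conflicts are minor.

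- **Overdose.** The definitions differ by 3 days (gaps of 8, 9 and 10 days). Separately, the SAP makes every case an SAE where the protocol does not. The supported effect is on the SAE listing. An effect on SAE tables or on recorded seriousness is inference. No event count can be given.
- **In-window dosing.** The documents support neither the claim that on-schedule dosing is never flagged nor the claim that it is. The answer depends on whether ± 3 days is measured between doses or around scheduled days.
- **Lack of efficacy.** The contradiction is direct and lies within the supplied protocol. Its reach is narrow, because COPD worsening has its own rule.

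The primary endpoint, sample size and 24-hour AESI notification are unaffected. The overdose comparison assumes that the supplied protocol's wording is still in force, which amendment 7 must confirm. This review does not say which interval is right.

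**What to change.** 1. Check the overdose and Appendix 3 wording in protocol amendment 7 first.
2. Reconcile the overdose interval so that SAP 2.4.3.2 and protocol 8.3.1 use one definition, and state whether the ± 3-day allowance is measured between doses or around scheduled days.
3. Reconcile the seriousness rule. Either replace the automatic-SAE sentence in SAP 2.4.3.2, so that overdose listings use the seriousness recorded on the AE eCRF under Appendix 3 (consistent with SAP Table 2 and Section 2.4.5.1), or reconcile the protocol to the SAP rule.
4. Reconcile the two lack-of-efficacy bullets in Appendix 3 so that one rule remains.

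The cost is a few sentences in SAP 2.4.3.2 and the protocol, plus a short clarification to sites. Design, sample size and efficacy analyses do not change.

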2.4.4 Analyses of efficacy endpoints

2.4.4.1 Analysis of primary efficacy endpoint(s)

Primary efficacy variable

The primary efficacy variable is annualized rate of moderate or severe COPD exacerbations over the 52-week treatment period compared to placebo.

The following null hypothesis and alternative will be tested for dupilumab arm against placebo:

- H0: No treatment difference between the dupilumab dose regimen and placebo in annualized rate of COPD exacerbation.
- H1: There is a treatment difference between the dupilumab dose regimen and placebo in annualized rate of COPD exacerbation.

Primary statistical model (ITT analysis)

The primary analysis of the annualized rate of moderate or severe exacerbation events during the 52-week placebo-controlled treatment period is to assess the efficacy of dupilumab in an intention-to-treat setting. Adjudicated COPD exacerbation events data will be used. Patients who permanently discontinue the study medication will be encouraged to return to the clinic for all remaining study visits. If a patient stays in study until the end of 52-week treatment period, all moderate or severe exacerbation events that happen up to Visit 16 will be included in the primary analysis, regardless if the patient is on treatment or not. And the observation duration is defined as from randomization to Visit 16 (Week 52). If a patient withdraws from study prior to the end of 52-week treatment period, all observed moderate or severe exacerbation events up to the last contact date or the end date of the planned 52-week treatment period (whichever is earlier) will be included in the analysis, and the observation duration is defined as from randomization to the last contact date or the end date of the planned 52-week treatment period whichever is earlier. No

imputation will be performed for the unobserved events that may happen after study discontinuation and up to Week 52. This estimand compares the rates of moderate or severe exacerbation for the patients randomized to the dupilumab and placebo arms, regardless of what treatment patients actually received. It assesses the benefits of the treatment policy or strategy relative to placebo (6).

The annualized rate of moderate or severe COPD exacerbation events will be analyzed using a negative binomial regression model. The model will include the total number of events occurred during the 52-week planned treatment period as the response variable, with the treatment group, region (pooled country), ICS dose at baseline (high dose ICS [yes/no]), smoking status at screening (current smokers or not), baseline disease severity (as % predicted post-bronchodilator FEV1), and number of moderate or severe COPD exacerbation events within one year prior to the study (≤ 2 , 3, or ≥ 4) as covariates. Log-transformed observation duration will be used as offset variable. The estimated annualized event rate for each treatment group and its two-sided 95% confidence intervals will be derived. The event rate ratio of the dupilumab group against placebo, its two-sided 95% confidence interval and p-value will be provided.

The rate difference between dupilumab and placebo, two-sided 95% confidence intervals of the rate difference and its p-value derived using delta method will also be provided as supportive information.

The analysis model will be built with the following sample SAS code:

```
proc glimmix data=event;
  class ics trt01pn cntygr1n smoking copdnum;
  model numevents=tr t01pn cn tygr1n ics smoking fev1bl copdnum
  /offset=logdu r dist=negbin link=log solution;
run;
```

If the model fails to achieve convergence, different estimation algorithms will be applied following the order: default→LAPLACE→QUAD (7). If the issue still exists, other handling may be considered. The adjustment will be added to the footnote of the corresponding outputs.

The gross estimated annualized event rate will also be presented by treatment group.

Mean cumulative function plot will be provided for descriptive purpose.

Sensitivity analysis

If patients withdraw from the study before Visit 16 (Week 52), moderate or severe exacerbation events that may occur after study discontinuation will not be observed. These patients are considered as patients with missing data on moderate or severe exacerbation. Number of patients with missing data, reasons and timing for patient withdrawals will be summarized by treatment groups. Summary statistics of selected demographic and baseline disease characteristics will be provided for patients with missing data and patients with complete data separately. In addition, the

following sensitivity analyses will be conducted to assess the robustness of the conclusion based on the primary analysis.

Pattern mixture model - multiple imputation (PMM-MI)

For each patient with missing data of moderate or severe exacerbation events, individual bi-weekly event probability will be estimated using observed data with adjustment of the planned treatment group, region (pooled country), ICS dose at baseline (high dose ICS [yes/no]), smoking status at screening (current smokers or not), baseline disease severity (as % predicted post-bronchodilator FEV1), and number of moderate or severe COPD exacerbation events within one year prior to the study (≤ 2 , 3, or ≥ 4). The total number of AECOPD moderate or severe events (on bi-weekly basis) will be calculated based on data imputed using multiple imputation.

Control-based PMM-MI

For each patient with missing data of moderate or severe exacerbation events, individual bi-weekly event probability will be estimated using observation in the placebo arms only, with adjustment of region (pooled country), ICS dose at baseline (high dose ICS [yes/no]), smoking status at screening (current smokers or not), baseline disease severity (as % predicted post-bronchodilator FEV1), and number of moderate or severe COPD exacerbation events within one year prior to the study (≤ 2 , 3, or ≥ 4). The total number of AECOPD moderate or severe events (on bi-weekly basis) will be calculated based on data imputed using multiple imputation.

Tipping point analysis

For each patient with missing data of moderate or severe exacerbation events, the bi-weekly event will be imputed in a similar fashion as PMM-MI based on various odds values. If the patient is on dupilumab, the predicted odds will be increased; if the patient is on Placebo, the predicted odds value will be decreased. The adjusted rate will then be used to impute the number of events that would occur during the missing observation period. A sequence of increasing/decreasing ratio will be used to generate different imputed datasets.

For each of the above methods, a negative binomial model will be fitted using each of the complete datasets composed of observed and imputed data, including the total number of observed and imputed events during the 52 weeks as the response variable, with the treatment group, region (pooled country), ICS dose at baseline (high dose ICS [yes/no]), smoking status at screening (current smokers or not), baseline disease severity (as % predicted post-bronchodilator FEV1), and number of moderate or severe COPD exacerbation events within one year prior to the study (≤ 2 , 3, or ≥ 4) as covariates. Log transformed observation duration will be the offset variable for patients who complete the 52-Week treatment/study period, and log transformed 52 weeks will be the offset variable for patients who discontinue the study before Visit 16 (Week 52). SAS MIANALYZE procedure will be used to generate statistical

inferences by combining results from the analysis with each dataset using Rubin's formula.

More details of the imputation and analyses methods are provided in Appendix J:

Subgroup analyses

To assess the consistency in treatment effects across different subgroup levels, subgroup analyses will be conducted for the primary efficacy endpoint with respect to:

- Age group (<65, ≥65 years)
- Gender (Male, Female)
- Region
- Territory
- Race (Caucasian/White, Black/of African descent, Asian/Oriental, Others)
- Ethnicity (Hispanic or Latino, Not Hispanic or Latino)
- Baseline weight (<70, ≥70- < 90, ≥ 90 kg; <60, ≥ 60 kg)
- Baseline BMI (<25, ≥25- <30, ≥30 kg/m²)
- ICS high dose level at baseline (Yes, No)
- Smoking status at screening (current smokers, former smokers)
- Number of moderate-or-severe COPD exacerbation events within one year prior to V1 (≤2, 3, or ≥4)
- Number of severe COPD exacerbation events within one year prior to V1 (0, 1, ≥ 2)
- Baseline predicted post-bronchodilator FEV1% (<50%, ≥50%)
- Baseline pre-bronchodilator FEV1 (< median, ≥ median)
- Baseline FEV1 reversibility (<12%, ≥ 12%; < median, ≥ median)
- Baseline fractional exhaled nitric oxide (FeNO) (<20, ≥ 20 ppb)
- Baseline eotaxin-3 (< median, ≥ median)
- Baseline IgE (< 100 , ≥ 100 IU/ml)
- Baseline PARC (< median, ≥ median)
- Baseline Fibrinogen (< 350, ≥ 350 mg/dL)
- Baseline mMRC (< median, ≥median)
- Maximum eosinophils counts during screening (≥ 0.3-<0.5, ≥0.5 Giga/L)

Treatment by subgroup interaction and its p-value will be derived from a negative binomial model. This model will include the total number of events occurring during the observation period as the response variable, with the two treatment groups, region (pooled country), ICS dose at baseline

(high dose ICS [yes/no]), smoking status at screening (current smokers or not), baseline disease severity (as % predicted post-bronchodilator FEV1), and number of moderate or severe COPD exacerbation events within one year prior to the study (≤ 2 , 3, or ≥ 4), subgroup (if different than the aforementioned covariates) and treatment by subgroup interaction as covariates. Log transformed observation duration will be the offset variable. If quantitative treatment by subgroup interaction is detected with nominal p-value < 0.05 for any subgroup factor, the Gail-Simon test will be performed to evaluate possible qualitative interaction. Summary statistics of moderate or severe exacerbations will be provided within each subgroup. Forest plot of relative risks and corresponding CIs and forest plot of risk differences and corresponding CIs comparing dupilumab dose group vs. placebo for the subgroups will be provided.

